7.1.2 Standard of Care Study Procedures

N/A

7.2 Laboratory Procedures/Evaluations

N/A

7.2.1 Clinical Laboratory Evaluations

N/A

7.3 Study Schedule

7.3.1 Screening

The participating dental provider will conduct chairside screening to determine patient eligibility for participation.

Screening Visit (Day 1)

- Obtain informed consent of potential subject verified by signature on written informed consent for screening form.
- Review medical history to determine eligibility based on inclusion/exclusion criteria.
- Review medications history to determine eligibility based on inclusion/exclusion criteria.

7.3.2 Enrollment/Baseline

Enrollment/Baseline Visit (Visit 1, Day 0)

CONFIDENTIAL

This material is the property of the NYU School of Medicine and Langone Medical Center. Do not disclose or use except as authorized in writing by the study sponsor
Interventional Template Version: 28 APR 2017

The dental resident or dentist subject screens the patient subject for oral cancer via use of an intraoral camera and the tele-mentoring protocol during her/his regularly scheduled dental visit.

7.3.3 Final Study Visit

The dental resident or dentist subject discusses the next steps with the patient subject, including scheduling a follow-up visit, where indicated.

7.4 Safety Oversight

It is the responsibility of the Principal Investigator to oversee the safety of the study at her site. This safety monitoring will include careful assessment and appropriate reporting of adverse events as noted above, as well as the construction and implementation of a site data and safety-monitoring plan. Medical monitoring will include a regular assessment of the number and type of serious adverse events.

No DSMB will be convened for this pilot study.

8 Clinical Monitoring

Clinical site monitoring is conducted to ensure that the rights and well-being of human subjects are protected, that the reported trial data are accurate, complete, and verifiable, and that the conduct of the trial is in compliance with the currently approved protocol/amendment(s), with GCP, and with applicable regulatory requirement(s).

No independent clinical monitor will be assigned for this pilot study.

9 Statistical Considerations

Feasibility Data Analysis

Provider Survey. All quantitative analyses will be conducted by [name] under the direction of [name]. Endorsement of 8 of the 10 checklist items (80%) by the provider subjects will be considered as the feasibility criterion. Specifically, [name] will estimate the average checklist endorsement score across all dentists with its associated 95% confidence interval (CI); if the upper bound of the CI exceeds 80%, we will consider the process to be feasible.

Provider Semi-Structured Interview. All interviews will be transcribed by a transcription company and coded by 2 research staff members ([name] and [name]). The research staff members will code individually and then meet to discuss and agree upon the final codes. The analysis of the qualitative data will utilize the techniques of narrative analysis and be guided by the constant comparison analytic approach to identify themes.

Acceptability Data Analysis

Patient Exit Survey. The acceptability criterion of the intervention will be that 80% or more of patients rate all 5 administered acceptability questions as “strongly agree” or “agree” on a Likert Scale.

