2.4.2 Known Potential Benefits

By participating in the proposed research, research subjects may gain the benefit of augmented services to prevent and/or identify oral cancer. Some patients may individually experience no benefit. This study will yield knowledge regarding methods for increasing adherence to evidence-based guidelines for prevention of, screening for, and treatment of oral cancer. Overall, the benefits of understanding effective methods for helping patients reduce their risk of oral cancer far outweigh the remote possibility of a breach of confidentiality.

CONFIDENTIAL

This material is the property of the NYU School of Medicine and Langone Medical Center. Do not disclose or use except as authorized in writing by the study sponsor

Interventional Template Version: 28 APR 2017

3 Objectives and Purpose

The purpose of the proposed research project is to evaluate and enhance the feasibility and acceptability of integrating a tele-mentoring component into the identification of oral lesions at the 6 dental clinics of Family Health Centers at NYU Langone (FHC), a Federally Qualified Health Center (FQHC) in Brooklyn, NY.

The tele-mentoring intervention involves training dental faculty member subjects and resident subjects to use intraoral cameras to take photographs of oral lesions and place them in the Dentrix electronic health record (EHR), along with descriptions of the lesions. This information will then be sent via Dentrix EHR to [name], the Director of Oral Pathology at NYU Langone Hospital – Brooklyn, and an initial dummy code entry will be placed in the Dentrix EHR. For each patient with a detected lesion, [name] will then review the Dentrix EHR chart and the uploaded photograph(s) of the lesion(s) found and place his observations in the Dentrix EHR. Next, [name] will discuss his findings with the involved dental faculty member / dental resident via secure NYU Langone Health e-mail. The dental provider will then enter an apt comment in the Dentrix EHR, using the following template: “Reviewed entry and contacted patient. Follow-up appointment needed / not needed (+ date) for an appointment on (date).” A second dummy code entry will then be placed in the patient chart in the Dentrix EHR. Once a week, [name] will receive a Dentrix EHR report with the 2 affiliated dummy codes for the tele-mentoring pilot study, and assure that entries for both codes are entered, and the loop is closed.

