Using a mixed-methods approach, we will evaluate and enhance the feasibility and acceptability of integrating a tele-mentoring component into the identification of oral lesions at the 6 FHC dental clinics. This will be achieved through:

1. Administering provider surveys (n=12) that consist of a checklist of 10 key components of the intervention based on process, and asking the dental provider subjects at each of the 6 FHC dental sites if each one was covered.
2. Conducting semi-structured interviews (n=6) with dental resident subjects at each of the 6 FHC sites to assess specific barriers to sustaining the intervention and strategies for addressing these barriers to facilitate integration of the intervention into the routine workflow of the dental clinics. The interviews will be informed by the Consolidated Framework for Implementation Research (CFIR)¹ and the Implementation Outcomes Framework (IOF).²
3. Administering brief exit interviews (n=30) with patient subjects at each of the 6 FHC dental sites regarding the acceptability of the intervention. The survey will assess patient satisfaction with the use of intraoral cameras at chairside to screen for and refer patients with oral lesions and identification of these oral lesions via tele-mentoring with an oral pathology expert ([name]).

Impact: If this pilot study proves successful, NYU Langone Health is well-equipped with both teaching and organizational expertise in faculty development activities, as well as the existing NYU Langone Dental Medicine national network of video-teleconferencing and web-based educational technology, to scale-up the proposed oral pathology asynchronous tele-mentoring educational program for the teaching of dental educators and residents, with the ultimate goal of improving patient care.

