4.2.2 Secondary Study Endpoints

Acceptability will be assessed using patient exit interviews (PEIs) conducted right after the dental visit is completed.

CONFIDENTIAL

This material is the property of the NYU School of Medicine and Langone Medical Center. Do not disclose or use except as authorized in writing by the study sponsor

Interventional Template Version: 28 APR 2017

Acceptability data collection.

Research staff will conduct a brief exit interview with 5 patients at each of the 6 FHC dental clinics with language interpretation services available regarding the acceptability of the intervention. We developed five statements on patient satisfaction with the intraoral cameras and the overall tele-mentoring intervention that will constitute the PEI. Patients will be asked the extent to which they agree with each statement (e.g., “Dentists should discuss with me ways to prevent and screen for oral cancer.”) (strongly agree, agree, disagree, strongly disagree). The acceptability criterion of the intervention will be that 80% or more of patients rate all five administered acceptability questions as “strongly agree” or “agree.” We will evaluate acceptability as described above for feasibility.

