5.6 Total Number of Subjects and Sites

All subjects will be recruited at the 6 FHC dental clinics in Brooklyn, NY.

The number of patient subjects will total 30 (5 from each of 6 FHC dental clinics).

The number of non-patient subjects will total 18: 12 dental resident and dentist subjects who will complete provider surveys (feasibility checklists), and 6 dental resident subjects who will complete semi-structured interviews.

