7.1 Study Procedures/Evaluations

7.1.1 Study Specific Procedures

The protocol for the tele-mentoring study was designed by Drs. [name] and [name], and is provided on the following page. This workflow will be refined based upon the results of the planned feasibility and acceptability testing. All study activities will take place in the 6 FHC dental clinics and private offices of NYU Langone Dental Medicine in Brooklyn, NY. The PEIs with patient subjects and the feasibility checklists with provider subjects will take 10-15 minutes to complete. The semi-structured interviews with dental resident subjects will take 30-45 minutes to complete, and will be digitally recorded and transcribed. The transcriptions will be stored in a secure REDCap database. The digital files will be deleted once they are transcribed. No identifying information will be recorded.

A2. Data Collection

[figure not shown]
Feasibility of the integrated intervention will be assessed through dental provider surveys and semi-structured interviews. The dental provider survey, which consists of a checklist of 10 key components of the tele-mentoring intervention to be implemented, will be completed by 2 dentists at each of the 6 FHC dental clinics (n=12) after screening at least 1 patient subject for oral cancer using an intraoral camera, as per the tele-mentoring protocol. Furthermore, after we have reached our target of 30 patient participants (5 patient participants at each of the 6 FHC dental sites), we will engage 6 dental residents (1 at each of the 6 FHC dental clinics) in a semi-structured interview to assess specific barriers they have encountered to sustaining the intervention and strategies for addressing those barriers to facilitate integration of the tele-mentoring intervention into the routine workflow of the dental clinics.

Acceptability of the integrated intervention will be assessed through brief patient exit surveys. Consented participants will be asked to complete a brief patient exit survey at the end of their dental appointments after being screening for oral cancer lesions using an intraoral camera.

The protocol for the tele-mentoring study is provided below:

CONFIDENTIAL

This material is the property of the NYU School of Medicine and Langone Medical Center. Do not disclose or use except as authorized in writing by the study sponsor
Interventional Template Version: 28 APR 2017

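### The 95% CI makes no allowance for clinic: it is too narrow if the pilot is to inform scale-up, yet widening it under the upper-bound rule would only make passing easier

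*Combined protocol and SAP*

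**What the plan says.** **Sampling.** Recruitment is by clinic. Under Section 7.1.1 the provider survey "will be completed by 2 dentists at each of the 6 FHC dental clinics (n=12". Section 5.6 states: "The number of patient subjects will total 30 (5 from each of 6 FHC dental clinics".

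**Feasibility (primary).** Under Section 9, Provider Survey, the analyst "will estimate the average checklist endorsement score across all dentists with its associated 95% confidence interval (CI", and the rule is: "if the upper bound of the CI exceeds 80%, we will consider the process to be feasible". Section 4.2.1 gives the same rule.

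**Acceptability (secondary).** Section 9, Patient Exit Survey, gives a point criterion and no CI: "The acceptability criterion of the intervention will be that 80% or more of patients rate all 5 administered acceptability questions" favourably. A CI enters only through one sentence in Section 4.2.2: "We will evaluate acceptability as described above for feasibility".

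**Target.** The purpose in Section 3 concerns "integrating a tele-mentoring component into the identification of oral lesions at the 6 dental clinics of Family Health Centers at NYU Langone (FHC", and all 6 clinics take part. The Impact paragraph of the same section looks further: if the pilot succeeds, the institution is equipped "to scale-up the proposed oral pathology asynchronous tele-mentoring educational program".

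**Not stated.** The documents give no CI formula, variance estimator, handling of clinic, ICC or standard deviation (SD) of the checklist score. Section 9.1 says that no sample size calculation is made.

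**The concern.** People in one clinic share operatories, camera set-up, workflow and staff, and the patients are screened by the same few providers. Their answers may therefore be alike. An average across individuals with an ordinary CI counts 12 and 30 separate pieces of information where there may be fewer.

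The feasibility verdict is read off a CI bound, so the width of the interval enters the decision. The plan does not say how that width is obtained. A result such as 18/30 patients, judged by the upper bound, fails with one defensible interval and passes with another. A pilot used to argue for scale-up would also report more precision than it has about other sites.

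**Working it through.** **Inputs.** Providers: 6 clinics × 2 = 12 (Section 7.1.1). Patients: 6 × 5 = 30 (Section 5.6). Threshold 80% and 95% CI (Sections 4.2.1 and 9), taken as two-sided. Assumed, because the documents give neither: ICC 0.05 to 0.30 and checklist SD 15 percentage points. The plan has no power or CI-width figure to reproduce; its counts agree.

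**1. Design effect.** DE = 1 + (m − 1) × ICC, effective n = n/DE, and CI width grows by √DE.

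| ICC | Providers (m = 2): DE, effective n, widening | Patients (m = 5): DE, effective n, widening |
|---|---|---|
| 0.05 | 1.05, 11.4, 2.5% | 1.2, 25.0, 9.5% |
| 0.10 | 1.10, 10.9, 4.9% | 1.4, 21.4, 18% |
| 0.20 | 1.20, 10.0, 9.5% | 1.8, 16.7, 34% |
| 0.30 | 1.30, 9.2, 14% | 2.2, 13.6, 48% |

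At 24/30 the Wald half-width is 1.96 × √(0.8 × 0.2/30) = 14.3 points. It becomes 14.3 × √1.4 = 16.9 at ICC 0.1 and 14.3 × √2.2 = 21.2 at ICC 0.3.

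**2. Coverage of the simple 95% CI, by simulation.** Providers: normal scores with a random clinic effect, t interval on 11 df. Patients: beta-binomial, true rate 80%, Wald interval.

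| ICC | Providers | Patients |
|---|---|---|
| 0.05 | 94.5% | 92% |
| 0.10 | 94.0% | 90% |
| 0.20 | 92.7% | 85% |
| 0.30 | 91.3% | 80% |

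These figures treat the 6 clinics as a sample of clinics. With the 6 clinics as the whole target (normal outcomes, both group sizes), coverage over the same ICC range is 95.4% to 97.4%, so the simple interval is then slightly too wide. At ICC 0 it is correct on either reading.

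**3. Effect on the upper-bound rule.** For patients the upper bound is p + 1.96 × √(p(1 − p)/30) × √DE:
- ICC 0: 19/30 gives 0.633 + 0.172 = 0.806 (pass); 18/30 gives 0.600 + 0.175 = 0.775 (fail).
- ICC 0.1: 18/30 gives 0.600 + 0.175 × 1.183 = 0.807 (pass).
- ICC 0.3: 17/30 gives 0.567 + 0.177 × 1.483 = 0.830 (pass).

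Clopper-Pearson limits give the same counts (19, 18, 17); Wilson limits give 20, 19 and 18.

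For providers at SD 15, the lowest passing mean is 80 − 2.201 × 15/√12 = 80 − 9.5 = 70.5%. Multiplying the half-width by √1.1 or √1.3 gives 70.0% or 69.1%.

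**4. The clinic-level interval.** Take the 6 clinic means or proportions and use t on 5 df. For providers it holds 95% coverage at every ICC. For patients at a true 80% it reaches 92% (ICC 0.1) and 88% (ICC 0.3), against 90% and 80% for Wald.

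**5. Interval and rule together.** Suppose true acceptability is 65%. At ICC 0.1 the upper-bound rule passes 63 to 64% of the time with the simple Wald CI and 82% with the clinic-level CI. At ICC 0.3 the figures are 61% and 91%. Requiring 24/30 instead passes about 10% of the time at ICC 0.1.

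**The case against.** **Independence is never stated.** The plan names no variance, so an unstated method is not a stated wrong one. This stands as far as it goes. An ordinary interval is the natural reading of a plain average with its CI, but the firm finding is that the method and the handling of clinic are missing.

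**The 6 clinics may be the target.** The purpose in Section 3 names them and all take part, so they can be regarded as fixed strata, and then the simple interval is not too narrow. This also stands. It leaves the scale-up aim in the same section, for which between-clinic variation counts. Even a clinic-level interval would be a weak basis for that, since nothing describes the 6 clinics as a sample of other sites.

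**The primary endpoint barely moves.** With 2 providers per clinic the passing mean shifts by 1.4 points at most (70.5% to 69.1%, ICC 0.3) through the design effect. This is correct; the larger effects concern the secondary endpoint.

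**Two stronger inferences are tempting and fail.** A reader might infer that both verdicts rest on intervals that are too narrow. Section 9 decides acceptability on a point proportion, which CI width cannot change; only the cross-reference in Section 4.2.2 brings in a CI. A reader might also infer that a narrow CI leads to a false claim of feasibility. The rule passes on the upper bound, so a narrow CI makes passing harder.

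**Conclusion.** The point holds conditionally. The plan samples in fixed groups from 6 clinics and makes no allowance for clinic. If ICC exceeds 0 and the result is to inform use beyond these clinics, a simple CI overstates precision: modestly for the 12 providers and materially for the 30 patients. The size depends on an assumed ICC; the documents supply none.

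The upper-bound rule is the larger defect, because it rewards imprecision. Correcting the interval while keeping that rule would make the plan more lenient. The change is worth making before analysis, provided that both parts are made together.

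**What to change.** In Sections 4.2.1, 4.2.2 and 9:

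- State the target of inference: these 6 clinics, or clinics more widely.
- Report the 6 clinic values. Give the 95% CI from the 6 clinic means (providers) or proportions (patients), with t on 5 df, as the measure of precision. With equal group sizes the point estimate does not change.
- Base the verdict on the point estimate reaching 80%, not on the upper bound. Do not adopt the wider CI while the upper-bound rule remains.
- Reconcile the cross-reference in Section 4.2.2 with the point criterion in Section 9, which 24/30 meets.

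A lower-bound rule is not a workable substitute: with 30 patients it would need 29/30 or 30/30, and could not be met at ICC 0.3.

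**Cost.** A few sentences and no new data. The drawbacks:
- If clinics do not differ, the provider interval is somewhat wider, with an average half-width of about 10.6 against 9.3 points at SD 15.
- Five df is few, and patient coverage is only partly restored (92% and 88%).
- Upper limits can exceed 100% and need truncating; at a true 80% and ICC 0.1 this happens in 57% of simulated trials.
- The point rule is stricter. At a true rate of exactly 80% with independent patients, 24 or more of 30 occurs with probability 0.61, against 0.99 for 19 or more.

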9.1 Sample Size

No sample size calculation will be conducted for this pilot study.

CONFIDENTIAL

This material is the property of the NYU School of Medicine and Langone Medical Center. Do not disclose or use except as authorized in writing by the study sponsor
Interventional Template Version: 28 APR 2017

10 Source Documents and Access to Source Data/Documents

Source data is all information, original records of clinical findings, observations, or other activities in a clinical trial necessary for the reconstruction and evaluation of the trial. Source data are contained in source documents. Examples of these original documents, and data records include: hospital records, clinical and office charts, laboratory notes, memoranda, subjects' diaries or evaluation checklists, pharmacy dispensing records, recorded data from automated instruments, copies or transcriptions certified after verification as being accurate and complete, microfiches, photographic negatives, microfilm or magnetic media, x-rays, subject files, and records kept at the pharmacy, at the laboratories, and at medico-technical departments involved in the clinical trial. It is acceptable to use CRFs as source documents. If this is the case, it should be stated in this section what data will be collected on CRFs and what data will be collected from other sources.

The study case report form (CRF) is the primary data collection instrument for the study. All data requested on the CRF must be recorded. All missing data must be explained. If a space on the CRF is left blank because the procedure was not done or the question was not asked, write "N/D". If the item is not applicable to the individual case, write "N/A". All entries should be printed legibly in black ink. If any entry error has been made, to correct such an error, draw a single straight line through the incorrect entry and enter the correct data above it. All such changes must be initialed and dated. DO NOT ERASE OR WHITE OUT ERRORS. For clarification of illegible or uncertain entries, print the clarification above the item, then initial and date it.

Access to study records will be limited to IRB-approved members of the study team. The investigator will permit study-related monitoring, audits, and inspections by the IRB/EC, the sponsor, government regulatory bodies, and University compliance and quality assurance groups of all study related documents (e.g. source documents, regulatory documents, data collection instruments, study data etc.). The investigator will ensure the capability for inspections of applicable study-related facilities (e.g. pharmacy, diagnostic laboratory, etc.).

Participation as an investigator in this study implies acceptance of potential inspection by government regulatory authorities and applicable University compliance and quality assurance offices.

11 Quality Assurance and Quality Control

QC procedures will be implemented beginning with the data entry system and data QC checks that will be run on the database will be generated. Any missing data or data anomalies will be communicated to the site(s) for clarification/resolution.

Following written SOPs, the monitors will verify that the clinical trial is conducted and data are generated, documented (recorded), and reported in compliance with the protocol, GCP, and the applicable regulatory requirements (e.g., Good Laboratory Practices (GLP), Good Manufacturing Practices (GMP)).

The investigational site will provide direct access to all trial related sites, source data/documents, and reports for the purpose of monitoring and auditing by the sponsor, and inspection by local and regulatory authorities.

CONFIDENTIAL

This material is the property of the NYU School of Medicine and Langone Medical Center. Do not disclose or use except as authorized in writing by the study sponsor

Interventional Template Version: 28 APR 2017

12 Ethics/Protection of Human Subjects

